6.2. Timing of Analyses

The final analysis will be performed after database lock when all subjects have been followed through Visit 7 (Week 24), the final study visit, at Day 168 (Window: Days 161-175).

6.3. Analysis Populations

6.3.1. Safety Analyses

All safety analyses will be performed in the safety analysis population. The safety population includes all randomized subjects who received at least one dose of study product. In the unlikely event of an error in randomization or study product administration (i.e., incorrect product), subjects will be grouped by the product they actually received.

6.3.2. Efficacy Analyses

All efficacy analyses will be performed in the Intent-to-Treat, Modified Intent-to-Treat, Complete Case, and Per Protocol analysis populations. For analyses of cumulative BV recurrence at Visit 4 or Visit 7 in all efficacy populations, subjects who withdraw or are withdrawn from study participation prior to the visit of interest and the reason for withdrawal recorded on the CRF is lack of treatment effect are included in the analysis population as experiencing recurrent BV at the point in time of the withdrawal. Likewise, for analyses of cumulative BV recurrence at Visit 4 or Visit 7 in all efficacy populations, subjects who discontinue study product prior to the visit of interest and the reason for discontinuation recorded on the CRF is lack of treatment effect or begin other treatment for BV prior to the visit of interest are included in the analysis population as experiencing recurrent BV at the point in time of the discontinuation or commencement of the other treatment.

See Section 6.5 for the imputation methods that will be used in the efficacy analyses.

6.3.2.1. Intent-to-Treat Analysis (ITT) Population

The ITT analysis population includes all randomized subjects, regardless of whether they received study treatment or were compliant with the administration procedures or schedule. In the unlikely event of an error in randomization or study product administration (i.e., incorrect product), subjects will be grouped by their intended randomized assignment.

6.3.2.2. Modified Intent-to-Treat (mITT) Population

The mITT population includes all randomized subjects who did not have any concomitant vaginal or cervical infections at screening or enrollment, received at least one dose of study product, and returned for at least one post-baseline visit prior to or including the visit of interest. In the unlikely event of an error in randomization or study product administration (i.e., incorrect product), subjects will be grouped by their intended randomized assignment.

Note this differs from what is stated in Section 11.6.2 of the protocol. See Section 13 for more details.

For efficacy analyses at Visit 4 (Week 12), subjects who discontinue prior to Visit 4, as well as subjects with a missing or non-evaluable Amsel or Nugent result at Visit 4 with no positive result at another visit, are included in the mITT population using imputation methods noted in Section 6.5.

For efficacy analyses at Visit 7 (Week 24), subjects who discontinue prior to Visit 7, as well as subjects with a missing or non-evaluable Amsel or Nugent result at Visit 7 with no positive result at another visit, are included in the mITT population using imputation methods noted in Section 6.5.

6.3.2.3. Complete Case (CC) Population

For efficacy analyses at Visit 4 (Week 12), the CC population includes all subjects who did not have any concomitant vaginal or cervical infections at screening or enrollment, received study product, and were followed up until the first diagnosis of BV or through Visit 4 (Week 12).

Note this differs from what is stated in Section 11.6.2 of the protocol. See Section 13 for more details.

For efficacy analyses at Visit 7 (Week 24), the CC population includes all subjects who did not have any concomitant vaginal or cervical infections at screening or enrollment, received study product, and were followed up until the first diagnosis of BV or through Visit 7 (Week 24).

In the unlikely event of an error in randomization or study product administration (i.e., incorrect product), subjects will be grouped by the product they actually received.

Subjects who terminate early prior to the visit of interest for reasons other than lack of treatment effect with no positive result at another visit, as well as subjects with a missing or non-evaluable Amsel or Nugent result with no positive result at another visit, are excluded from the CC population.

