5.3.2 Masking Procedures

At the time of enrollment, the site pharmacist will select the next available box of study product applicators in sequential order and will distribute to masked study personnel with no labels that identify the product or applicators as LACTIN-V or placebo. No masking procedures are required for the MetroGel.

The site pharmacist, participants, study personnel who perform study assessments, data entry personnel at the sites, and laboratory personnel performing study assays will be masked to treatment assignment. The Data and Safety Monitoring Board (DSMB) may receive data in aggregate and presented by treatment group, but without the treatment group identified. The DSMB may be unmasked to individual study treatment assignments, as needed, to adequately assess safety issues. Refer to the MOP for unmasking procedures, including emergency unblinding procedures.

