6.1.2 Formulation, Packaging, and Labeling

LACTIN-V and placebo

Each applicator will contain a LACTIN-V powder formulation containing *L. crispatus* CTV-05 at a potency of 2×10^9 cfu/dose. [REDACTED]

. A

matching placebo formulation without *L. crispatus* CTV-05 is supplied in an identical applicator containing placebo powder.

LACTIN-V or placebo pre-filled applicators will be individually packaged in heat-sealed foil pouches, each containing one desiccant packet. Each participant will receive one box containing 25 applicators. Each foil pouch and box will be labeled with the study number and unique participant number.

The foil pouches and boxes will be labeled by the Osel Study Product Supplier. Each label will contain the study number and the FDA-required cautionary statement "*Caution- New drug -Limited by Federal Law to Investigational Use.*" The label of each box of study product applicators will also include the unique participant number and the statements: "*Store at home in a cool, dry place out of reach of children (at room temperature).*"

MetroGel vaginal gel

MetroGel vaginal gel is a gelled purified water solution, containing metronidazole at a concentration of 7.5 mg/g (0.75%). The gel is formulated at pH 4.0. The gel also contains carbomer 934P, edetate disodium, methylparaben, propylparaben, propylene glycol and sodium hydroxide.

MetroGel vaginal gel is supplied in a 70 gram tube. Each participant will receive one box of MetroGel vaginal gel sufficient for the 5-day course of treatment.

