9. Participants will be reminded to abstain from sexual intercourse for 12 hours after each study product application and for 12 hours before the remaining study visits at Visit 3 (Week 8, Day 56), Visit 4 (Week 12, Day 84) and Visit 7 (Week 24, Day 168).
10. Participants will receive non-spermicidal lubricated condoms for their male sexual partners. Participants will be encouraged to use condoms if they engage in vaginal intercourse through Visit 7 (Week 24, Day 168).
11. Participants will be asked if they still have the remaining applicators for the twice weekly doses stored at home. If not, they will receive additional pre-filled applicators to administer twice weekly through week 11. Participants will be instructed to transport the pre-filled applicators while avoiding exposure to high temperatures.

12. Participants will be instructed to collect all used applicators and store them as described in the MOP and to return all used applicators at their next visit, Visit 3 (Week 8, Day 56).
13. Applicators used since the last study visit will be collected. Applicators will be stained and tested as described in the MOP.
14. An appointment for the follow-up visit will be scheduled. Depending on the time of the enrollment and the average length of the participant's menstrual cycle, careful attention should be paid to the approximate time of the participant's next menstrual period when scheduling those visits. Later adjustments of those dates may be necessary.

Women with vaginal discharge or vaginitis symptoms who were diagnosed with yeast on the wet mount during the follow-up visit will be referred for standard treatment and continue to receive study product.

If the test results at the follow-up visit suggest a urinary tract infection, cervicitis or vulvovaginitis, the participant will be referred for standard treatment and continue to receive study product.

If the clinician suspects the woman to have developed an STI since the last visit, appropriate tests will be conducted and if needed the woman will be referred to standard of care treatment in compliance with current CDC STD Treatment Guidelines. The participant should be treated in case of positive findings and continue to use study product.

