11.6.2 Data Analysis Populations

The safety population will include all randomized participants who received study treatment.

The Modified Intent-To-Treat (mITT) population will include all randomized participants who met all inclusion/exclusion criteria, received study product, and returned for at least one post-baseline visit.

The Complete Case (CC) population will include all participants in the mITT population who were followed up until the first diagnosis of BV or through Visit 4 (Week 12, Day 84), or discontinued from the study as a treatment failure. The CC population will be used as the primary efficacy analysis population for the test of LACTIN-V to placebo.

The Per-Protocol (PP) population will include all randomized participants who met all inclusion/exclusion criteria, complied with the assigned study product, were followed up until the first diagnosis of BV or through Visit 4, or discontinued from the study as a treatment failure.

A participant is compliant with the assigned study product if she takes at least 75% of the scheduled doses prior to the first diagnosis of BV or through Visit 4 (Week 12, Day 84).

Prior to unblinding, a blinded case review committee will review participants with a reported concomitant infection/disease/procedure that may interfere with study product, use of concomitant medications or products that may interfere with study product, significant protocol deviations, and other events that may impact study product effectiveness or study analyses. On a case-by-case basis, the case review committee will determine if each participant will be included in PP population, if and when a participant should be censored or removed from PP analyses, and/or any other analytical requirements for the participant.

For the primary efficacy analysis participants who discontinue for reasons other than lack of treatment effect, as well as participants with a missing or non-evaluable Amsel or Nugent result with no positive result at another visit, are

excluded from the CC and PP populations, but included in the mITT population using imputation methods noted in Section 11.6.4.1.

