6.5. Missing Data

The primary efficacy outcome measure of BV recurrence will be assessed in the CC population. Use of the mITT population has previously been recommended by the FDA where missing values from subjects who drop out early are imputed using Last Observation Carried Forward (LOCF) [6]. However, this includes subjects who dropped out after completing at least one-follow-up visit, and/or before their first positive diagnosis. LOCF would classify such subjects as ‘not recurrent.’ Thus, it is possible that the estimated proportions of treatment successes in a study arm could, in reality, be larger than expected. Thus, LOCF could result in an over-optimistic estimate of treatment effect, conflicting with the following rationale for using an ITT analysis population stated in ICH E9 [7]: “[ITT analysis] tends to avoid over-optimistic estimates of efficacy resulting from a per protocol analysis, since the non-compliers included in the [ITT] analysis set will generally diminish the estimated treatment effect.” In addition, simulation studies suggest that CC analysis leads to slightly less biased estimates of the difference in cure proportions (LACTIN-V vs. placebo) compared to the mITT analysis using LOCF.

To assess the effect of the choice of analysis population on the primary analysis, the analysis will be repeated as a secondary analysis in the ITT, mITT, and PP populations. The following imputation methods will be used for BV recurrence by Visit 4 and BV recurrence by Visit 7 in the ITT and mITT populations:

- LOCF
- Worst-Case Scenario – impute missing/unevaluable values in the LACTIN-V group as treatment failures and missing values in the Placebo group as treatment successes.

For summaries of recurrence in “by study day” displays, missing data will not be imputed.

For the secondary analyses of successful *L. crispatus* colonization by Visit 4 and by Visit 7, missing or unevaluable colonization data at a visit will imputed as unsuccessful colonization. For summaries of colonization in “by study day” displays, missing data will not be imputed.

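### If a randomisation or product error occurs, the primary Complete Case analysis would group women by product received, not by randomised arm

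*SAP*

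**What the plan says.** Both documents make CC the primary efficacy set. Protocol 11.6.2 states: "The CC population will be used as the primary efficacy analysis population for the test of LACTIN-V to placebo". SAP 6.5 agrees: "The primary efficacy outcome measure of BV recurrence will be assessed in the CC population".

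The rule for a product or randomisation error, which the SAP calls unlikely, differs by population:

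- **ITT (SAP 6.3.2.1) and mITT (SAP 6.3.2.2):** "subjects will be grouped by their intended randomized assignment".
- **CC (SAP 6.3.2.3):** "subjects will be grouped by the product they actually received". The Table 6 footnote repeats the as-received basis for CC.
- **Safety and PP (SAP 6.3.1 and 6.3.2.4):** also as received.

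Protocol 11.6.2 builds CC from mITT ("The Complete Case (CC) population will include all participants in the mITT population") and does not say how women given the wrong product are grouped.

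On supply, Protocol 6.1.2 says "Each participant will receive one box containing 25 applicators". Protocol 7.3 covers women who no longer hold their remaining applicators: "If not, they will receive additional pre-filled applicators to administer twice weekly through week 11". Protocol 7.4 (by reference) and 7.10 repeat this, and SAP 4.4.3 provides more doses to women who overuse. Neither document says how these extra applicators are matched to the woman's arm.

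**The concern.** As-received grouping is usual for safety. In a superiority test of efficacy it assigns women to arms on an event that happens after randomisation, so for any woman affected the comparison loses the protection that randomisation gives.

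Two further problems follow. SAP 6.5 repeats the primary analysis in ITT, mITT and PP to show how much the choice of population matters. If CC and mITT also assign the same woman to different arms, a difference between them mixes the handling of missing data with a change of arm. And a woman who has used both products has no single product received, and the SAP gives no rule for placing her.

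**Working it through.** **1. Planned size.** Inputs from Protocol 11.4 and SAP 5: recurrence 30% on placebo, a 50% reduction (so 15% on LACTIN-V), allocation 2:1, 10% drop-out, power 70%. The test is two-sided Pearson chi-square at 5% (Protocol 11.3).

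Pooled rate p̄ = (0.30 + 2 × 0.15)/3 = 0.20.

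n(placebo) = [1.960 × √(p̄(1 − p̄)(1 + 1/2)) + 0.524 × √(0.30 × 0.70 + 0.15 × 0.85/2)]² / 0.15²
= (0.960 + 0.274)² / 0.0225 ≈ 67.7, so 68.

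Total 3 × 68 = 204; 204/0.90 = 226.7, so 227. The plan's 228 is the next multiple of 3 and is reproduced. Expected evaluable women: 228 × 0.90 = 205.2, about 137 and 68, with power 70.4%. The grouping rule does not affect these figures.

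**2. What one regrouped woman does.** X² = (pL − pP)² / [p̄(1 − p̄)(1/nL + 1/nP)], without continuity correction. The counts are hypothetical, at the planned evaluable size. Moving a woman leaves the overall 205 unchanged.

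| Case | LACTIN-V | Placebo | X² | p |
|---|---|---|---|---|
| Near the threshold | 24/137 | 20/68 | 3.81 | 0.051 |
| One recurrent woman, LACTIN-V to placebo | 23/136 | 21/69 | 4.97 | 0.026 |
| One recurrent woman, placebo to LACTIN-V | 25/138 | 19/67 | 2.81 | 0.094 |

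The design rates imply 0.15 × 137 = 20.6 and 0.30 × 68 = 20.4 recurrences, about 21 and 20:

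| Case | LACTIN-V | Placebo | p |
|---|---|---|---|
| About the design rates | 21/137 | 20/68 | 0.018 |
| Recurrent, LACTIN-V to placebo | 20/136 | 21/69 | 0.008 |
| Recurrent, placebo to LACTIN-V | 22/138 | 19/67 | 0.037 |
| Not recurrent, LACTIN-V to placebo | 21/136 | 20/69 | 0.022 |
| Not recurrent, placebo to LACTIN-V | 21/138 | 20/67 | 0.014 |

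No single move crosses 0.05 there. The margin is thin: from 22/137 vs 20/68 (p = 0.026), moving one recurrent placebo woman gives 23/138 vs 19/67, p = 0.052.

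**3. With no error.** Product received equals product assigned for every woman, the two groupings coincide, and the effect is zero.

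**The case against.** The rule is conditional, and the SAP expects the condition to be rare. There are also safeguards. Listing 2 names every woman whose product differs from her assignment. Table 11 shows ITT and mITT by randomised arm beside CC, so a result driven by regrouping should be noticed. The case review committee (SAP 6.3.2.5), blinded to treatment and to BV outcome, can decide inclusion, censoring and other handling for any efficacy population. CC already conditions on follow-up after randomisation. These points stand and limit the size. They do not remove the defect: ITT and mITT are secondary, no as-randomised CC result is planned, and the committee has no written rule for a woman who used both products.

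A reader might infer three stronger things that the documents do not support.

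- **That re-supply is a likely source of wrong product.** If spare applicators came from the next box in a 2:1 sequence, they would be the wrong product with probability 1/3 for LACTIN-V women and 2/3 for placebo women, or 2/3 × 1/3 + 1/3 × 2/3 = 4/9 overall. But the rule that "the site pharmacist will select the next available box of study product applicators in sequential order" is limited to the time of enrolment; nothing extends it to re-supply. Pouches and boxes carry a participant number (Protocol 6.1.2), logs are required (Protocol 6.3), and masked staff can dispense coded kits matched to arm. The MOP may specify this and is not available here. Nor do the documents show that a later woman's box would be depleted.
- **That the SAP silently departs from the protocol.** SAP Section 13 does not mention the grouping rule, but Protocol 11.6.2 is silent on it, so the SAP can be read as filling a gap.
- **That the comparison is biased.** Purely random mis-supply with a clear single-product rule would not by itself bias it. Bias needs errors that differ between arms, or a lopsided rule for mixed exposure.

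**Conclusion.** The point holds on the text of SAP 6.3.2.3. The primary efficacy set is grouped differently from ITT and mITT, and in the event of a product or randomisation error the primary test is not a comparison of the randomised arms.

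The size depends wholly on whether errors occur, and the documents give neither an error rate nor a re-supply rate. Close to the 5% threshold a single regrouped woman can change the conclusion; at about the design rates (21/137 vs 20/68) she cannot. The numerical examples assume the planned 137 and 68 evaluable women and illustrative event counts. This is an inexpensive safeguard for the primary test, not a demonstrated bias.

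**What to change.** In SAP 6.3.2.3, group CC by randomised assignment, as for ITT and mITT. Change the CC rows and footnote of Table 6, and the description of that table in SAP 6.3.2.6, to match. Keep as-received grouping for Safety, and for PP if wanted, with a stated rule for women who used both products. Make the change before unblinding. It needs about one sentence and a footnote, no new data and no change to the sample size of 228.

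Separately, check in the MOP how applicators re-supplied under Protocol 7.3, 7.4 and 7.10 and SAP 4.4.3 are matched to the randomised arm. If it is covered there, a cross-reference is enough; if not, the procedure should be written down.

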3.3. Study Definitions and Derived Variables

3.3.1. BV Diagnosis

The Amsel criteria and Nugent score will be used to diagnose BV.

During a pelvic examination, presence of the following Amsel criteria will be determined:

- a. Homogeneous, thin, grayish-white discharge that smoothly coats the vaginal walls
- b. Vaginal pH > 4.5
- c. Positive whiff-amine test, defined as the presence of a fishy odor when a drop of 10% potassium hydroxide (KOH) is added to a sample of vaginal discharge
- d. Presence of clue cells (>20%) on microscopy

A vaginal swab for assessment of BV by Nugent criteria will be performed. The Nugent score utilized a 0-10-point scale for evaluation of vaginal flora. The Nugent score is interpreted as follows:

- 0-3 Normal
- 4-6 Intermediate
- 7-10 BV

A positive diagnosis of BV is defined by the presence of at least three of the Amsel criteria and a Nugent score of 4 or greater.

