6.3.2.4. Per Protocol (PP) Population

For the analyses at Visit 4 (Week 12), the PP population includes all randomized subjects who met all inclusion/exclusion criteria at enrollment, complied with the assigned study product, and were followed up until the first diagnosis of BV or through Visit 4 (Week 12).

For the analyses at Visit 7 (Week 24), the PP population includes all randomized subjects who met all inclusion/exclusion criteria at enrollment, complied with the assigned study product, and were followed up until the first diagnosis of BV or through Visit 7 (Week 24).

In the unlikely event of an error in randomization or study product administration (i.e., incorrect product), subjects will be grouped by the product they actually received.

Subjects who terminate early prior to the visit of interest for reasons other than lack of treatment effect with no positive result at another visit, as well as subjects with a missing or non-evaluable Amsel or Nugent result with no positive result at another visit, are excluded from the PP population.

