		Did not receive study product	x	x	x	x	x	x
		Did not return for at least one post-baseline visit	x	x	x	x	x	x

Notes: N=number of enrolled subjects.
Treatment group is the treatment group to which a subject was randomized.

Table 6: Safety, Complete Case, and Per Protocol Analysis Populations for Safety and Primary Analysis by Treatment Group

Analysis Population	Eligibility Category	Reason Subjects Excluded	LACTIN-V (N=X)		Placebo (N=X)		All Subjects (N=X)	
			n	%	n	%	n	%
Safety Analysis Population	Eligible for Safety		x	x	x	x	x	x
	Excluded from Safety	Any Reason	x	x	x	x	x	x
		Did not receive study product	x	x	x	x	x	x
Complete Case (CC) Analysis Population	Eligible for CC		x	x	x	x	x	x
	Excluded from CC	Any Reason	x	x	x	x	x	x
		Did not meet inclusion/exclusion criteria	x	x	x	x	x	x
		Did not receive study product	x	x	x	x	x	x
		Was not followed up until the first diagnosis of BV or through Visit 4 (Week 12, Day 84)	x	x	x	x	x	x
Per-Protocol (PP) Analysis Population	Eligible for PP		x	x	x	x	x	x
	Excluded from PP	Any Reason	x	x	x	x	x	x
		Did not meet inclusion/exclusion criteria	x	x	x	x	x	x
		Was not compliant with study product	x	x	x	x	x	x
		Was not followed up until the first diagnosis of BV or through Visit 4 (Week 12, Day 84)	x	x	x	x	x	x

Notes: N=number of enrolled subjects.

Treatment group is the actual treatment a subject received

Table 7: Summary of Halting Rules - Safety Population

Halting Rules	Number of Subjects
One or more subjects experiences a treatment-related SAE	x
Two or more subjects experience treatment-related vulvar and/or vaginal ulceration, abscess, or necrosis	x
Four or more subjects experience a treatment-related severe (Grade 3) systemic adverse event	x
An overall pattern of symptomatic, clinical, or laboratory events that the DMID Medical Monitor or DSMB consider associated with study drug and that may appear minor in terms of individual events, but that may collectively represent a serious potential concern for safety	x

Table 8: Ineligibility Summary of Screen Failures

Inclusion/Exclusion Category	Inclusion/Exclusion Criterion	Number of Subjects ^a
Inclusion and Exclusion	Any Criterion	x
Inclusion	Any inclusion criterion	x
	[inclusion criterion 1]	x
	[inclusion criterion 2]	x
	[inclusion criterion 3]	x
Exclusion	Any exclusion criterion	x
	[exclusion criterion 1]	x
	[exclusion criterion 2]	x
	[exclusion criterion 3]	x
Declined Enrollment	Any Reason	x
	Time commitment	x
	Concern of potential risks	x
	Number of procedures	x

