LACTIN-V/Placebo	LACTIN-V/Placebo	xxxxxx	[e.g., Safety, ITT, mITT, CC, PP]	[e.g., Safety, ITT, mITT, CC, PP, Visit x]	Yes/No	xxxxxx
LACTIN-V/Placebo	LACTIN-V/Placebo	xxxxxx	[e.g., Safety, ITT, mITT, CC, PP]	[e.g., Safety, ITT, mITT, CC, PP, Visit x]	Yes/No	xxxxxx
LACTIN-V/Placebo	LACTIN-V/Placebo	xxxxxx	[e.g., Safety, ITT, mITT, CC, PP]	[e.g., Safety, ITT, mITT, CC, PP, Visit x]	Yes/No	xxxxxx

Note: “Yes” in the “Results available” column indicates that available data were removed from the analysis. If “Yes” the population in which data were removed will be listed in parenthesis. “No” indicates that no data were available for inclusion in the analysis.

Implementation Notes:

1. Sort order will be actual treatment group, Subject ID
2. Reasons Subject Excluded should match the same verbiage that is used on the Analysis population tables
3. If all subjects received the correct treatment, only display “Treatment Group”.

Listing 2 Subjects Whose Assigned Treatment Group Does Not Match Their Randomized Treatment Group

Subject ID	Treatment Group at Randomization	Treatment Actually Received
xxxxxx	LACTIN-V/Placebo	LACTIN-V/Placebo
xxxxxx	LACTIN-V/Placebo	LACTIN-V/Placebo

Implementation Note:

1. Sort order is Subject ID.

Listing 3 Early Terminations or Discontinued Subjects-All Enrolled Subjects

Actual Treatment Group	Randomized Treatment Group	Subject ID	Category	Study Day Corresponding to Early Termination/Treatment Discontinuation/Completion	Reason for Early Termination/ Treatment Discontinuation
LACTIN-V/Placebo	LACTIN-V/Placebo	XXXXXXXX	Early Termination/Treatment Discontinuation/Completion	xx	XXXXXXXXXXXXXXXXXXXX
LACTIN-V/Placebo	LACTIN-V/Placebo	XXXXXXXX	Early Termination/Treatment Discontinuation/Completion	xx	---

Implementation Notes:

1. Sort order will be by Actual Treatment Group, Subject ID, Category
2. Category will be "Early Termination", "Completion" or "Treatment Discontinuation". If a subject discontinued treatment, they will have two records.
3. In the "Reason" column, concatenate any "specify" fields, including AE number and DV number.

Listing 4 Subject-Specific Protocol Deviations-All Enrolled Subjects

Deviation Number	Study Day	Deviation Description	Deviation Category	Reason for Deviation	Deviation Affected Product Stability?	Deviation Resulted in AE?	Deviation Resulted in Subject Termination?	Deviation Resolution	Comments
Actual Treatment Group: , Randomized Treatment Group: , Subject ID:									

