xx	xx	xxxxxxx	xxxxxxxxxxx	xxxxxxx	Yes/No	Yes/No	Yes/No	Yes/No	xxxxxxxxxxx
xx	xx	xxxxxxx	xxxxxxxxxxx	xxxxxxx	Yes/No	Yes/No	Yes/No	Yes/No	--

Note: Deviation description column will contain all subfields concatenated together

Implementation Notes:

1. Sort order will be by Actual Treatment Group, Subject ID, Deviation Number
2. In the Deviation Category column concatenate any specify fields
3. In the Reason for Deviation column concatenate any specify fields.

Listing 5 Non-Subject-Specific Protocol Deviations

Site	Deviation	Start Day	End Day	Reason for Deviation	Deviation Resulted in Subject Termination?	Deviation Affected Product Stability?	Deviation Category	Deviation Resolution	Comments
xxxx	xxxx	xx	xx	xxxx	Yes/No	Yes/No/NA	xxxx	xxxx	xxxx
xxxx	xxxx	xx	xx	xxxx	Yes/No	Yes/No/NA	xxxx	xxxx	xxxx

Note: Deviation column will contain all subfields concatenated together

Implementation Notes:

1. Sort order will be by Site Name, Start Date
2. In the Deviation Category column concatenate any specify fields
3. In the Reason for Deviation column concatenate any specify fields.

Listing 6 Individual Efficacy Response Data

Study Day (Week)	Homogeneous, thin, grayish-white discharge	Vaginal pH	Amine (“whiff”) test on KOH wet mount	Clue Cells on wet mount (%)	Amsel Criteria	Nugent Score	BV Diagnosis	L. crispatus Concentration (copies/mL)	CTV-05 Concentration (copies/mL)	Lactobacillus spp. Concentration (copies/mL)	Total Bacteria Concentration (copies/mL)	L. crispatus Colonization Status
Actual Treatment Group: , Randomized Treatment Group: Subject ID:												
x (x)	Present/ Absent/ Not Assessed	xx.x	Negative/ Positive/ Not Assessed	xx	x	x	Positive/ Negative/ Indeterminate	x.x E x	x.x E x	x.x E x	x.x E x	Successful/ No colonization

Implementation Notes:

1. Sort order is actual treatment group, Subject ID, Study Day.
2. If all subjects received the correct treatment, only display “Treatment Group”.

Listing 7 Compliance Data- All Treated Subjects

Actual Treatment Group	Subject ID	Week	Dose	Dose Taken? (Subject Report)	Study Day of Administration (Subject Report)	Time of Administration (Subject Report)	Number of Applicators Returned (Used / Unused)	Staining Assessment (Used / Unused / Indeterminate)	Compliance Status
xxxxxx	xxxxxx	1	1	Yes/No	xx	xx:xx	x / x	x / x / x	Compliant/Non-compliant
			2	Yes/No	xx	xx:xx			
			3	Yes/No	xx	xx:xx			
			4	Yes/No	xx	xx:xx			
			5	Yes/No	xx	xx:xx			
		2	1	Yes/No	xx	xx:xx	x / x	x / x / x	

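### The Complete Case and Per Protocol rules exclude, and the worst-case rule scores as LACTIN-V failures, women whose visit is already BV-negative on one observed component

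*SAP*

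**What the plan says.** SAP 3.3.1 gives a conjunctive outcome: a positive diagnosis is "defined by the presence of at least three of the Amsel criteria and a Nugent score of 4 or greater".

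For the primary population, SAP 6.3.2.3 states that "subjects with a missing or non-evaluable Amsel or Nugent result with no positive result at another visit, are excluded from the CC population". SAP 6.3.2.4 repeats this for the Per Protocol (PP) set: "subjects with a missing or non-evaluable Amsel or Nugent result with no positive result at another visit, are excluded from the PP population". Protocol 11.6.2 has the same rule for both sets, beginning "participants with a missing or non-evaluable Amsel or Nugent result with no positive result at another visit, are". None of the three names the visit at which the missing result counts. The mITT definition in SAP 6.3.2.2 does: it covers "subjects with a missing or non-evaluable Amsel or Nugent result at Visit 4 with no positive result at another visit", and sends those women to the imputation methods of SAP 6.5.

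SAP 6.5 uses LOCF and a worst-case rule for ITT and mITT. Worst case scores missing or unevaluable LACTIN-V results as failures and missing placebo results as successes.

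On reporting, Listing 6 shows the diagnosis as "Positive/ Negative/ Indeterminate", with no rule separating the last two categories. Below its total, the Table 6 mock-up gives three reasons for Complete Case (CC) exclusion: eligibility, no study product, and not followed to a first BV diagnosis or Visit 4. The implementation notes to Listing 1 add: "Reasons Subject Excluded should match the same verbiage that is used on the Analysis population tables".

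**The concern.** Because both components are required, a visit with Amsel 0 and an unreadable slide cannot be BV-positive. Nor can one with Nugent 2 and a missing wet mount. No section of either document turns this into a derived negative. A woman with such a Visit 4 and no positive elsewhere is dropped from the primary denominator although her status at that visit is known. In the worst-case rows, if she is on LACTIN-V, she becomes a recurrence that her own data rule out.

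Without a named visit, the CC and PP rules could also be programmed so that a missing component at Week 4 removes a woman with a complete negative Visit 4. Visit 4 is the natural reading, but the text does not fix it.

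At stake are a few women in the primary denominator, the level of the reported rates, and the meaning of the worst-case bound.

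**Working it through.** **The plan's own figure.** Inputs from SAP 5 and 6.1: 30% versus 15% recurrence, two-sided 5%, 70% power, 2:1 allocation, 10% loss from CC. The pooled rate is (0.30 + 2×0.15)/3 = 0.20. Placebo n = [1.960×√(0.20×0.80×1.5) + 0.524×√(0.21 + 0.1275/2)]² / 0.15² = 67.7, so 68. With 136 on LACTIN-V the total is 204, and 204/0.9 gives 227, or 228 as a multiple of 3. Power at 228×0.9 = 205.2 evaluable is 70.4%. The stated 228 and 70% reproduce.

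**Assumptions, none given in the documents.**
- m: share unevaluable at Visit 4, taken as 2% to 5%.
- f: share of recurrers positive only at Visit 4.
- s: share of unevaluable non-recurrers whose observed component is negative.

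**Women lost from CC.** With 137 and 68 evaluable, expected non-recurrers are 137×0.85 + 68×0.70 = 164.05. At 2% the rule drops 3.3 and at 5% it drops 8.2. Some may already sit within the planned 10%. If 8.2 are lost on top of it, about 197 remain and power is 68.7%.

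**Rates under the current rule.** The CC rate is p(1−fm) / [p(1−fm) + (1−p)(1−m)].

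| m | f | Placebo (true 30%) | LACTIN-V (true 15%) |
|---|---|---|---|
| 2% | 0 | 30.4% | 15.3% |
| 5% | 0 | 31.1% | 15.7% |
| 5% | 1/3 | 30.7% | 15.4% |
| 5% | 2/3 | 30.4% | 15.2% |
| 5% | 1 | 30.0% | 15.0% |

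With equal m and f in both arms, the odds in each arm are multiplied by the same (1−fm)/(1−m), so the odds ratio (OR) stays at 0.412. At f = 0 and 5% versus 1% unevaluable it becomes 0.43 (more on LACTIN-V) or 0.40 (more on placebo).

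**Worst-case ITT row.** With 152 and 76 randomised and 10% missing in each arm:
- LACTIN-V: (0.15×136.8 + 15.2)/152 = 0.235.
- Placebo: 0.30×68.4/76 = 0.27.
- OR = (0.235/0.765)/(0.27/0.73) = 0.83.

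Known-negative LACTIN-V women among the missing number 137×0.85×m×s. At m = 5% this is 1.46 (s = 25%) to 5.82 (s = 100%), and scoring them correctly gives OR 0.79 to 0.66. At m = 2% it is 0.58 to 2.33, giving 0.81 to 0.76. Taking the 5% of all 152 instead gives at most 6.46 women and OR 0.64. Placebo does not move, because its missing results already count as successes.

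**Effect of correct scoring on CC.** If the remaining indeterminate women are excluded, the rate is p(1−fm) / [p(1−fm) + (1−p)(1−m(1−s))]. If they are counted as recurrent, it is p + (1−p)m(1−s). Placebo at m = 5%:

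| f | s | Current rule | Indeterminate excluded | Indeterminate counted recurrent | OR, excluded / recurrent |
|---|---|---|---|---|---|
| 1/3 | 100% | 30.7% | 29.6% | 30.0% | 0.412 / 0.412 |
| 1/3 | 50% | 30.7% | 30.2% | 31.8% | 0.412 / 0.444 |
| 1/3 | 25% | 30.7% | 30.5% | 32.6% | 0.412 / 0.459 |
| 2/3 | 100% | 30.4% | 29.3% | 30.0% | 0.412 / 0.412 |

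**The case against.** The strongest reply is that the plan already keeps these women elsewhere. The LOCF rows of Table 11 retain them, and one with earlier negatives is scored non-recurrent, as the fix would score her. Assessors and laboratory are masked, so there is no evident reason for loss to differ by arm. This stands, and it is why the point is minor.

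A reader might infer that the report would hide how many women the rule removes. The documents do not support that. Table 6 has an any-reason CC total by arm. Listing 1 names each excluded woman and flags whether available data were removed. Listing 6 shows both components by visit, and Table 10 counts specimens not collected and results not obtained. What is missing is a tabulated count for this reason.

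A reader might also infer that the current rule always inflates recurrence. It does so only to the extent that recurrers are caught before Visit 4; at f = 1 there is no bias.

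The fix has its own cost. Readmitting observed negatives leaves the remaining exclusion on likely recurrers. At f = 2/3 and s = 100%, the CC placebo rate of 29.3% is further from 30% than the current 30.4%. With unequal loss (2% on LACTIN-V, 10% on placebo) and f = 2/3, the OR under the fix is 0.43 to 0.44 (s = 80% to 100%) against 0.40 now and a true 0.41. Counting indeterminate women as recurrent also pulls the OR towards 1 even under equal loss. That line therefore belongs in a sensitivity analysis, and only one CC result should be primary.

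Finally, worst case is meant to be harsh. That justifies assuming the worst about unknown outcomes, but not overriding a known one.

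**Conclusion.** The point holds as a minor defect in a stated rule. The outcome definition settles a one-component-negative visit, but the CC and PP rules discard it and the worst-case rule contradicts it for LACTIN-V. At an assumed 2% to 5% unevaluable, the primary analysis loses about 3 to 8 known or likely non-recurrers, and placebo reads at most 0.4 to 1.1 percentage points high. The CC OR does not move under equal loss, so the documents do not support reading this as a bias in the primary comparison. The largest effect is on the worst-case ITT OR: about 0.83 instead of roughly 0.79 to 0.66 at 5% unevaluable, depending on how many unevaluable women have an observed negative component. The text reading is firm. The sizes rest on rates that the documents do not give.

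**What to change.** 1. In SAP 3.3.1, score a visit BV-negative when either observed component is below threshold. Amsel counts as below threshold only if criteria marked not assessed could not bring it to three. Where the diagnosis cannot be settled, score the visit indeterminate.
2. Apply this derivation before the CC and PP exclusions, and before LOCF and worst-case imputation in SAP 6.5.
3. In SAP 6.3.2.3 and 6.3.2.4, name Visit 4 (or Visit 7 for the Week 24 analysis). Exclude a woman only when that visit is indeterminate or absent and no other visit is positive. Keep the SAP 6.3.2 rule that counts lack-of-effect withdrawals and discontinuations, and other BV treatment, as recurrence.
4. Keep one primary CC result, with indeterminate women excluded. Add one labelled sensitivity line counting them as recurrent.
5. Add a Table 6 row for indeterminate BV status at Visit 4, by arm, and record the change in SAP 13.

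The cost is a few sentences, one derivation, one table row and one sensitivity line, plus a possible small downward bias in the CC rates. No new data are needed, since Listing 6 already draws on each component by visit.

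Separately, SAP 6.3.2.5 lets the blinded committee act on all efficacy populations, while SAP 6.3.2.1 defines ITT as everyone randomised. State that the committee cannot remove any woman from ITT. This matters only if removals occur.
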